8.4. Relapse of disease

An event which is part of the natural course of the disease under study (i.e., disease relapse) is captured in the study as an efficacy measure; therefore it does not need to be reported as an SAE.

Relapse of the tumor will be recorded in the clinical assessments in the CRF. Death due to progressive disease is to be recorded on a specific form in the CRF but not as an SAE. However, if the progression of the underlying disease is greater than that which would normally be expected for the patient, or if the investigator considers that there was a causal relationship between treatment with the recMAGE-A3 + AS15 ASCI +/- Poly IC:LC or protocol design/procedures and the disease progression/recurrence, then this must be reported as an SAE.

Any new primary cancer (not related to the cancer under study) must be reported as an SAE.

8.5. Clinical laboratory parameters and other abnormal assessments qualifying as adverse events and serious adverse events

All laboratory results (normal and abnormal) will be recorded in the patient's CRF as described in the study procedures (Table 5 and Table 6).

Abnormal laboratory findings (e.g. clinical chemistry, haematology, urinalysis) or other abnormal assessments will be recorded as AEs or SAEs:

- If they occur after the start of protocol therapy and meet the definition of an AE, as defined in Section 8.1 or SAE, as defined in Section 8.2.
- If they are present at baseline and worsen outside the patient's usual range of fluctuations after the start of protocol therapy.

CONFIDENTIAL

- If they are associated with the disease being studied but are more severe than expected for the patient’s condition.

Abnormal laboratory findings (e.g., clinical chemistry, haematology, urinalysis) or other abnormal assessments will NOT be recorded as AEs or SAEs:

If they are present at baseline and DO NOT worsen outside the patient’s usual range of fluctuations after the start of protocol therapy. If they are associated with the disease being studied and are in line with what is expected for patient’s condition.

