A separate IND, No. 43,984, was opened in 1995 under which 6 clinical studies have thus far been conducted in approximately 350 glioma or glioblastoma patients. Dose regimens used in these trials generally consisted of 20- $\mu\text{g}/\text{kg}$ Poly-ICLC 3 times each week. The degree of adverse effects seen with of Poly-ICLC depends on 3 factors: (1) dose, (2) route of injection, and (3) health status of the patient. Early phase 1 studies were done to determine the maximum tolerated dose, under the assumption that this was also the most effective dose. In these studies of cancer patients, it was found that the maximum tolerated dose was about 12 mg/m^2 when given intravenously in patients who were not terminally ill. Patients typically developed fevers of 40°C, myalgias, arthralgias, malaise, and some nausea and vomiting. Fever was the primary dose-limiting factor. At this dose, the mean serum interferon level was 2000 IU/mL. While the dose of exogenous interferon rarely attains this level, levels of 100 IU/mL after exogenous interferon are associated with the same adverse effects as those in high-dose Poly-ICLC. In most of the early cancer trials, doses around 6 mg/m^2 of Poly-ICLC IV were generally used. Mild (grade 1), transient (less than 7 days) hepatic enzyme elevations were described in a trial of 100 $\mu\text{g}/\text{kg}$ Poly-ICLC given intravenously in multiple sclerosis patients. In 3 patients, the elevated enzyme levels were prolonged for greater than 7 days, but in all patients, the enzyme levels returned to normal after temporary discontinuation of the Poly-ICLC. One paralyzed multiple sclerosis patient in this group suffered a fatal pulmonary embolus that was not judged to be due to the drug. Poly-ICLC has been associated with a coagulopathy in dogs, but not in other species (including primates); and there has been no change in the expected incidence of deep venous thrombosis, pulmonary embolus, or coagulopathy in multiple sclerosis, AIDS, or malignant glioma patients on low-dose intramuscular Poly-ICLC. It was subsequently shown that a low dose of Poly-ICLC was better than a high dose for enhancing immune effects, and that the higher dose actually inhibited a number of cell-associated immune functions. It was also found that intramuscular injection brought about much milder side effects. Representative safety data in humans at a dose of 20- $\mu\text{g}/\text{kg}$ Poly-ICLC 3 times each week have been reported in 2 clinical trials: Protocol NABTC 01-05 entitled: "An open multicenter trial of Poly-ICLC treatment of newly diagnosed glioblastoma with Poly-ICLC as an adjuvant to external beam radiation" and Protocol NABTC 01-06 entitled: "An open multicenter trial of Poly-ICLC in subjects with recurrent anaplastic glioma." Treatment with Poly-ICLC in these 2 clinical trials appeared to be well tolerated; adverse reactions were usually mild or moderate in nature (grade 1 or 2 by the National Cancer Institute Common Terminology Criteria for Adverse Events scale).

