8. ADVERSE EVENTS AND SERIOUS ADVERSE EVENTS

The investigators are responsible for the detection and documentation of events meeting the criteria and definition of an adverse event (AE) or serious adverse event (SAE) as provided in this protocol. During the study, when there is a safety evaluation, the investigator or site staff will be responsible for detecting AEs and SAEs, as detailed in this section of the protocol.

Each patient or patient's guardians will be instructed to contact the investigator immediately should the patient manifest any signs or symptoms they perceive as serious.

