8.1. Definition of an adverse event

An AE is any untoward medical occurrence in a clinical investigation patient, temporally associated with the use of a medicinal product, whether or not considered related to the medicinal product.

An AE can therefore be any unfavorable and unintended sign (including an abnormal laboratory finding), symptom, or disease (new or exacerbated) temporally associated with the use of a medicinal product. For marketed medicinal products, this also includes failure to produce expected benefits (i.e., lack of efficacy), abuse or misuse.

Examples of an AE include:

- Exacerbation of a chronic or intermittent pre-existing condition including either an increase in frequency and/or intensity of the condition.
- New conditions detected or diagnosed after investigational product administration even though it may have been present prior to the start of the study.
- Signs, symptoms, or the clinical sequelae of a suspected interaction.
- Signs, symptoms, or the clinical sequelae of a suspected overdose of either investigational product or a concurrent medications (overdose per se should not be reported as an AE/SAE).
- Signs, symptoms temporally associated with treatment administration.
- Blood counts or chemistries that were abnormal at baseline and worsen outside the patient's usual range of fluctuations after the start of protocol therapy Examples of an AE DO NOT include: Medical or surgical procedure (e.g., endoscopy, appendectomy); the condition that leads to the procedure is an AE.
- Situations where an untoward medical occurrence did not occur (social and/or convenience admission to a hospital).
- Anticipated day-to-day fluctuations of pre-existing disease(s) or condition(s) present or detected at the start of the study that do not worsen.
- The disease/disorder being studied, or expected progression, signs, or symptoms of the disease/disorder being studied, unless more severe than expected for the patient's condition.
- Blood counts or chemistries that were abnormal at baseline and did not worsen outside the patient's usual range of fluctuations after the start of protocol therapy AEs may include pre- or post-treatment events that occur as a result of protocol-mandated procedures (i.e., invasive procedures, modification of patient's previous therapeutic regimen).

Example of events to be recorded in the medical history section of the CRF:

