10.1.1. Safety and tolerability endpoints

Occurrence of adverse events up to 30 days after each study dose, including abnormal haematological and biochemical parameters.

Occurrence of serious adverse events and autoimmunity during the whole study duration (up to 30 days after the last administration of study treatment). For methods of analysis, see Section 10.7.5.

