10.7.5.1. Adverse events

Adverse events (AEs), including abnormal laboratory values, will be graded according to the CTCAE, Version 4.0 and coded to the preferred term (PT) level using the MedDRA dictionary.

The percentage of patients with adverse event(s) within 30 days of each recMAGE-A3 + AS15 ASCI dose +/- Poly IC:LC will be reported by treatment group with exact 95% confidence intervals, as per MedDRA terminology, by Preferred Term (PT) and System Organ Class (SOC), if appropriate. The same tabulation will be presented for grade 3, grade 4, related, grade 3 related and grade 4 related events, if appropriate.

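### Whether a laboratory value abnormal at baseline counts as an adverse event rests on unblinded judgement of an undefined usual range; the likely effect is small and the remedy is one table

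*Combined protocol and SAP*

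**What the plan says.** **The rule.** Section 8.5 lists when a laboratory finding is recorded as an AE or SAE. A finding already abnormal at baseline qualifies if it worsens outside the patient's "usual range of fluctuations after the start of protocol therapy". The matching exclusion covers findings "If they are present at baseline and DO NOT worsen outside the" patient's usual range. Section 8.1 applies the same test in the AE definition: "Blood counts or chemistries that were abnormal at baseline and worsen outside the" patient's usual range. Section 8.5 also excludes, as AEs, disease-associated findings that are in line with the patient's condition.

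**The data.** Section 8.5 also states: "All laboratory results (normal and abnormal) will be recorded in the" CRF.

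**The endpoint and its analysis.** Section 10.1.1 defines the first safety endpoint as "Occurrence of adverse events up to 30 days after each study dose, including abnormal haematological and biochemical parameters". Section 10.7.5.1 says that AEs, "including abnormal laboratory values, will be graded according to the CTCAE, Version 4.0", and then reports the percentage of patients with events within 30 days of each dose, by arm, with exact 95% confidence intervals. Section 10.3 plans a toxicity table by category and worst grade for the two regimens. Under 10.6.3, a patient with no reported event is counted as having none.

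**Who decides.** Section 8.5 names nobody. Section 8 gives detection and documentation of AEs to the investigators and site staff, and 8.6 has the investigator evaluate each one. The synopsis states that the trial is open label.

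**The concern.** The two arms differ only by Poly IC:LC. Section 1.2.4 reports liver-enzyme elevations with that agent in an earlier trial, so an investigator may expect them in one arm and not in the other. If the same rise in a baseline-abnormal patient is reported in one arm and accepted as usual fluctuation in the other, the AE table shows a difference that comes from reporting. It could equally hide a real one.

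A value judged usual produces no AE record, and 10.6.3 then treats the patient as event-free. No planned table is clearly built from the laboratory values themselves, so the analysis would not reveal the discrepancy. A fixed grading scale applied to recorded values does not depend on this judgement.

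**Working it through.** The plan gives no figure on this point and no power for safety (10.3 limits power calculations to the immune endpoint), so there is no stated number to reproduce. The check is a comparison of the text, a comparison of dates, and a scale calculation.

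**1. Is the criterion defined?** Sections 8.1 and 8.5 give no number of prior values, no percentage change and no CTCAE grade shift. Table 5 schedules pre-dose haematology and chemistry only at S1 and S2, so the study itself holds at most two scheduled earlier values per patient. Older clinical records may exist, but the plan does not require their values in the CRF, so the judgement cannot be checked from trial data.

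**2. Can baseline-abnormal patients enter?** Yes. Section 4.2 admits transaminases up to 2.5 times the upper limit of normal, and bilirubin and creatinine up to 1.5 times. It sets no limit for LDH, alkaline phosphatase or lymphocytes, all of which are in Table 8. It admits M1c disease, which Appendix D defines to include any distant metastasis with elevated LDH. These are ceilings, and the documents do not say how many patients will be abnormal.

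**3. Do the analysis sections bypass the rule?** Not clearly. The wording of 10.1.1 and 10.7.5.1 could mean that abnormal values are counted directly. It could also mean only those that became AEs under 8.5. Section 10.3 places its worst-grade table under AE reporting and does not say that it uses CRF laboratory values. No shift table is specified.

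**4. How much laboratory data falls in the 30-day window?** Doses are given at weeks 0, 3, 6, 9 and 12, then every 12 weeks from week 24 to week 108 (Tables 5 and 6). Post-baseline haematology and chemistry are at Visits 5, 8, 12 and 14.

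| Visit | Week | Previous dose (week) | Days since previous dose |
|---|---|---|---|
| 5 | 12 | 9 | 3 × 7 = 21 |
| 8 | 48 | 36 | 12 × 7 = 84 |
| 12 | 96 | 84 | 12 × 7 = 84 |
| 14 | 120 | 108 | 12 × 7 = 84 |

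Only Visit 5 lies within 30 days of an earlier dose. Unscheduled tests, and any sample drawn after that day's dose, would be exceptions.

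**5. Scale of a reporting difference.** Let b be the share abnormal at baseline and w the share of those who worsen, both equal in the two arms, so that the true difference is zero. Let r₁ and r₀ be the shares reported in the Poly IC:LC and control arms. The spurious difference is b × w × (r₁ − r₀). All inputs are assumptions: w = 0.30, r₁ = 0.90, r₀ = 0.60.

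| b | Calculation | Difference (points) | Patients per 20 |
|---|---|---|---|
| 0.10 | 0.10 × 0.30 × 0.30 | 0.9 | 0.18 |
| 0.20 | 0.20 × 0.30 × 0.30 | 1.8 | 0.36 |
| 0.30 | 0.30 × 0.30 × 0.30 | 2.7 | 0.54 |
| 0.50 | 0.50 × 0.30 × 0.30 | 4.5 | 0.90 |

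The difference is proportional to the reporting gap and is zero if reporting is equal. For comparison, one recoded patient among 20 moves an arm's rate by 5 points: 2/20 = 10% (exact 95% CI 1.2% to 31.7%) becomes 3/20 = 15% (3.2% to 37.9%).

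**The case against.** The strongest reply is that this is ordinary AE practice with little reach. Investigator judgement enters every AE in the trial. Safety is unpowered and descriptive, and no between-arm test of AEs is specified. CTCAE grading and a worst-grade table are already planned. Grade 4 events are SAEs under 8.2, and 6.4.5 requires follow-up of clinically significant laboratory abnormalities. All of this stands and keeps the weight low. It does not remove the ungraded step that decides whether a baseline-abnormal value becomes an AE at all.

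Three stronger readings are tempting, and the documents do not support them.

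- **A large bias.** A reader might apply the 30% worsening rate to the whole arm and infer 0.30 × (0.90 − 0.60) = 9 points, or 0.30 × (0.90 − 0.40) = 15 points. The rule touches only patients abnormal at baseline, so these figures would require everyone to be so.
- **An expected liver signal here.** Section 1.2.4 says "In 3 patients, the elevated enzyme levels were prolonged for greater than 7 days", but it describes the elevations generally as grade 1 and lasting less than 7 days. They occurred in multiple sclerosis patients given 100 µg/kg intravenously, and the prolonged ones normalised after temporary discontinuation. Section 5.1.2 of this protocol describes 1 mg given deep subcutaneously. The passage supports an investigator's expectation and gives no rate for this trial. A rise lasting less than a week would mostly have gone by a sample 21 days after the dose.
- **Lost data.** The exclusion of disease-expected findings might be read as leaving them unrecorded. Section 8.5 excludes them only as AEs, and all results remain in the CRF. Patients are completely resected at entry and stop study treatment at relapse, so that clause has limited reach.

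It is also fair to say that a patient's usual range could draw on clinical records beyond S1 and S2. That makes the judgement possible, but still not reproducible from the trial database.

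**Conclusion.** The point holds as an improvement of small weight. A baseline-abnormal laboratory value is an AE only by an unblinded judgement against an undefined range, this feeds part of the primary safety endpoint, and the plan does not clearly analyse the recorded values independently. Sections 10.1.1 and 10.7.5.1 need reconciling with 8.5 in any case, since one reading counts abnormal values directly and the other does not.

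The plausible size is about 0.9 to 4.5 points between arms, which is less than one patient in 20. That rests on assumed shares: 10% to 50% abnormal at baseline, 30% of those worsening, and 90% against 60% reporting. The documents supply none of these, and they do not show that differential reporting will occur. With only Visit 5 scheduled inside the 30-day window, the exposure is narrower still. No sample size or power figure is affected.

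**What to change.** Keep the 8.5 rule for AE reporting. Add the following to 10.7.5.1:

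- a by-arm table, for each haematology and chemistry analyte in Table 8, of worst CTCAE v4.0 grade and shift from the last pre-dose value;
- computed from the CRF values whether or not an AE was reported, with shift against the laboratory reference range where no CTCAE grade applies;
- with results inside the 30-day window shown separately from those at Visits 8, 12 and 14, so that the 10.1.1 endpoint is not widened unnoticed.

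State in 10.1.1 and 10.7.5.1 whether the laboratory part of the endpoint means reported AEs or graded values, and cross-refer to 8.5.

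The cost is one programmed table from data already collected. It needs no new samples, visits or patients. The downside is that more low-grade abnormalities will be listed.

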8.6. Time period, frequency, and method of detecting adverse and serious adverse events

All AEs occurring within 30 days following administration of each dose of the study treatment must be recorded on the Adverse Event form in the patient's CRF, irrespective of intensity or whether or not they are considered to be related to the treatment administration.

The standard time period for collecting and recording SAEs (except autoimmune SAEs see below) will begin at randomization or the first receipt of study treatment and will end at the concluding visit (Visit 14, Month 30) or until 30 days after the administration of the last dose of study treatment in the event of early discontinuation of study treatment administration. See Section 8.9 for instructions on reporting and recording SAEs.

Onsets of potential immune mediated diseases (pIMD) or autoimmune disease occurring throughout the study (from Visit 1 until the end of the follow-up period) must be recorded as AE or SAE, as appropriate, in the patient CRF (see Section 8.3). Appropriate documentation of the diagnosis of autoimmune diseases must be provided in each instance.

An overview of the protocol-required reporting periods for adverse events and serious adverse events is given in Table 9.

Study activity	Screening phase	Treatment phase				Concluding visit	Follow-up
	From ICF signature to Visit 1	Visit 1	30 days post Visit 1	Visit X (X=2 to 13)	30 days post Visit X	Visit 14	Till 5 years after first administration or study withdrawal
Reporting of AEs ^a							
Reporting of SAEs ^a							
Reporting of autoimmune diseases							
Reporting of SAEs related to study participation and concurrent GSK medications ^b							

CONFIDENTIAL

- i. Except autoimmune AEs and SAEs which are reported till end of follow-up.
- j. Surgical resection of the tumor and adjuvant chemotherapy administration are not considered as study procedures; SAEs related to these treatments should not be recorded.

Table 10. Reporting periods for adverse events and serious adverse events

The investigator will inquire about the occurrence of AEs/SAEs and pIMD at every visit/contact during the study and throughout the follow-up period.

All AEs, either observed by the investigator or one of her/his clinical collaborators or reported by the patient spontaneously or in response to a direct question will be evaluated by the investigator. AEs not previously documented in the study will be recorded in the Adverse Event form within the patient's CRF. The nature of each event, date and time (where appropriate) of onset, outcome, intensity and possible relationship to treatment administration should be established. Details of any corrective treatment should be recorded on the appropriate page of the CRF. Refer to Section 5.8.

As a consistent method of soliciting AEs, the patient should be asked a non-leading question such as:

"Have you felt different in any way since receiving the treatment or since the previous visit?"

N.B. The investigator should record only those AEs having occurred within the time frame defined above. AEs already documented in the CRF, i.e. at a previous assessment, and designated as "not recovered/not resolved" or "recovering/resolving" should be reviewed at subsequent visits, as necessary. If these have resolved, the documentation in the CRF should be completed.

When an AE or a SAE occurs, it is the responsibility of the investigator to review all documentation (e.g., hospital progress notes, laboratory, and diagnostics reports) relative to the event. The investigator or designate will then record all relevant information regarding the AE/SAE on the CRF or SAE Report Form as applicable.

The investigator will attempt to establish a diagnosis of the event based on signs, symptoms, and/or other clinical information. In such cases, the diagnosis should be documented as the AE/SAE and not the individual signs/symptoms.

All SAEs will also be reported to the FDA directly by the sponsor, MCC. See section 8.9.1 for reporting of SAEs to GSK Bio and Oncovir.

8.7. Evaluating adverse events and serious adverse events

8.7.1. Assessment of intensity

Severity of AEs will be assessed according to the International Common Terminology Criteria for Adverse Events (CTCAE; version 4.0).

The investigator will make an assessment of intensity for all AEs, including SAEs reported during the study. The assessment will be based on the investigator's clinical judgment. The intensity of each AE and SAE recorded in the CRF will be graded according to the table given in the CTCAE (version 4.0; cf. Appendix F).

An AE assessed as Grade 3 (severe) should not be confused with a SAE. Grade 3 is a category utilized for rating the intensity of an event; and both AEs and SAEs can be assessed as Grade 3. An event is defined as 'serious' when it meets the definition in Section 8.2.

8.7.2. Assessment of causality

The investigator is obliged to assess the relationship between the investigational product and the occurrence of each AE/SAE. The investigator will use clinical judgment to determine the relationship. Alternative causes, such as natural history of the underlying diseases, concomitant therapy, other risk factors and the temporal relationship of the event to the investigational product will be considered and investigated. The investigator will also consult the Investigator Brochures and/or Product Information, for marketed products, in considering his/her assessment.

There may be situations when a SAE has occurred and the investigator has minimal information to include in the initial report to the FDA. However, it is very important that the investigator always makes an assessment of causality for every event prior to submission of the SAE to the FDA. The investigator may change his/her opinion of causality in light of follow-up information, amending the SAE information accordingly. The causality assessment is one of the criteria used when determining regulatory reporting requirements.

In case of concomitant administration of multiple treatments, it may not be possible to determine the causal relationship of general AEs to the individual treatments given. The investigator should therefore assess whether the AE could be causally related to treatment administration rather than to the individual treatments.

Causality of all AEs should be assessed by the investigator using the following question:

Is there a reasonable possibility that the AE may have been caused by the investigational product?

NO: The AE is not causally related to administration of the study treatment(s). There are other, more likely causes and administration of the study treatment(s) is not suspected to have contributed to the AE.

YES: There is a reasonable possibility that the treatment(s) contributed to the AE.

Non-serious and serious AEs will be evaluated as two distinct events. If an event meets the criteria to be determined “serious” (see Section 8.2 for definition of serious adverse event), it will be examined by the investigator to the extent to be able to determine ALL contributing factors applicable to each serious adverse event.

Other possible contributors include:

- Medical history
- Other medications
- Protocol required procedure
- Other procedure not required by the protocol
- Erroneous administration
- Other cause (specify)

